7.1.2 Health care resource utilisation

A description of health care resource utilisation variables for new users of the study medications will be presented as mean, standard deviation, median, interquartile range, and absolute and relative frequencies. The results will be presented for the overall population (Shell Table 4.1), for adults (Shell Table 4.2), and for those patients aged 40 years or older with a diagnosis of COPD (Shell Table 4.3). The variables and their definitions are listed in Section [5.3.2](#).

7.1.3 Severity of COPD

Severity of COPD will be described among patients aged 40 years or older with a diagnosis of COPD with or without a recorded diagnosis of asthma, as described in Section [5.1](#). Severity of COPD will also be described among patients aged 39 years or younger if there are more than 5 patients in each severity category. The definition of COPD severity is included in Section [5.3.4](#). Criteria used to define COPD severity in each data source will be also described. For each data source, the absolute and relative frequency of patients in each category of COPD severity, and criteria within each category of COPD severity, will be presented by study medication (Shell Table 9).

7.2 CONCOMITANT DISEASES AND MEDICATION

Frequency of history of specific diseases and conditions of interest at any time before the index date will be assessed for each exposure group in each data source within the overall study population (Shell Table 5.1 and Shell Table 6.1). The same analysis will be repeated for adults (Shell Table 5.2 and Shell Table 6.2) and for those patients aged 40 years or older with a diagnosis of COPD (Shell Table 5.3 and Shell Table 6.3). Diagnosis of COPD, asthma, and other respiratory comorbidities and time since first COPD diagnosis will be included as part of the description of medical history. In this table, COPD, asthma, and respiratory comorbidities will not be mutually exclusive, and a patient will be allowed to be in more than one group. The comorbidities to be considered are listed in Sections [5.3.4](#) and [5.3.5](#), and a complete list of codes is included in [Annex Table 1-5](#).

The number and percentage of patients with a prescription or dispensing for a specific medication within the year before the index date will be described in each exposure group for the overall population (Shell Table 7.1 and Shell Table 8.1), for all adults (Shell Table 7.2 and Shell Table 8.2), and for those patients aged 40 years or older with a diagnosis of COPD (Shell Table 7.3 and Shell Table 8.3). A description of the medications considered is detailed in Section [5.3.6](#), and the list of codes is presented in [Annex Table 1-6](#).

7.3 METHODS ADDRESSING BIAS

The exclusive use of hospital outpatient and/or inpatient discharge diagnoses can overestimate potential off-label prescribing because many patients with COPD may have never been hospitalised, and COPD is a disease that is mainly managed in the primary care setting. For this reason, to maximise the sensitivity and specificity of the algorithms, the algorithms to identify patients with COPD and asthma will be adapted to each data source (e.g., using inpatient records only or outpatient and inpatient records or using ICD-10 or thesaurus coding) and based on available data and prior experience in designing studies evaluating COPD and other diseases. “Potential COPD” and “other respiratory conditions” will be characterised to provide a description of “other potential uses” of olodaterol and indacaterol among those with no diagnosis of COPD or asthma. However, it is acknowledged that none of these other respiratory conditions is an approved indication for olodaterol or indacaterol, and that indication of the prescription will be unknown for a certain portion of patients.

7.4 METHODS ADDRESSING CONFOUNDING/EFFECT MEASURE MODIFICATION

Not applicable.

7.5 MAIN ANALYSES

7.5.1 Clinical indication and evaluation of off-label and potential off-label use

A detailed description of the definition of COPD indication and on-label and off-label use is presented in Section [5.1](#). The prevalence of on-label and off-label new users and 95% confidence interval will be presented for olodaterol and indacaterol. Confidence intervals will be calculated using the Clopper-Pearson method for the binomial distribution [[R06-1080](#)]. Patients will be classified hierarchically:

- 1. All children will be classified as off-label, irrespective of their diagnosis.
- 2. All adult patients with a diagnosis of COPD will be considered on-label irrespective of whether they have a diagnosis of asthma or any other respiratory condition.
- 3. All adults without a COPD diagnosis and with a diagnosis of asthma will be classified under the group of “asthma only,” irrespective of whether they have any other respiratory condition. These patients will be classified as off-label.
- 4. All adults with no COPD and no asthma diagnosis will be classified as potential off-label. Among these patients, “probable COPD” and “other respiratory conditions” will be described. These will not be mutually exclusive, patients can have one or more of the respiratory conditions listed and “probable COPD.” Patients with no “other respiratory conditions” and no “probable COPD” will be classified under “No history of recorded respiratory conditions and no probable COPD.”

Results for the main analysis will be presented overall (Shell Table 10.1) and separated by age group (< 18, 18-29, 30-39, 40-49, 50-59, 60-69, 70-79, 80+ years; Shell Tables 10.2 through 10.9).

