#### 9.3.2.1 On-label prescribing: indication of COPD

The indication of COPD is defined as any patient with a diagnosis of COPD, chronic bronchitis, or emphysema recorded in the database at any time before the index date or at the index date. Because COPD can occur in association with asthma, patients with a recorded diagnosis for both COPD and asthma will be considered on-label. [\[R14-0350\]](#) [\[R07-2620\]](#) [\[R08-1492\]](#).

For this study, classification of COPD status will be based on general practice diagnoses and hospital outpatient and inpatient discharge diagnoses. No validation data are available for COPD diagnoses recorded in PHARMO. In general, in Denmark and Sweden, validation has been performed for COPD diagnoses ascertained via hospital (inpatient and outpatient) diagnoses. ICD diagnoses codes for COPD have shown a good positive predictive value (PPV). In the Danish National Registers, the PPV for the hospital discharge diagnosis of COPD (ICD-10 code J44) was 92%. [\[R14-0359\]](#) In Sweden, a COPD validation study showed that the COPD diagnosis (ICD-9: 491-492, 496; ICD-10: J41-J44) recorded in the National Inpatient Registry was considered as proven in 21.7% of cases, probable in 35.5%, possible in 34.0%, uncertain in 2.1%, and unlikely in 7.0%. [\[R14-0456\]](#) The proportion of patients with asthma misclassified as having COPD was 2.1%, and the overall degree of misclassification was less than 10%. The registry was considered of acceptable validity for epidemiological research of COPD.

The ICD-10 and ICD-9 codes to identify the diagnosis of COPD are detailed in [Table 3](#). Diagnosis codes include COPD, chronic bronchitis, and emphysema.

Table 3 ICD-10 and ICD-9 diagnoses and codes to identify patients with COPD

| ICD-10 Code Description                     | ICD-10 Code | ICD-9 Code |
|---|-------------|------------|
| Chronic bronchitis                          | J41-J42     | 491        |
| Emphysema                                   | J43         | 492        |
| Other COPD                                  | J44         | 496        |
| COPD with acute lower respiratory infection | J44.0       | —          |
| COPD with acute exacerbation, unspecified   | J44.1       | —          |
| Other specified COPD                        | J44.8       | —          |
| COPD, unspecified                           | J44.9       | —          |

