## 9.4 DATA SOURCES

The study will be conducted in the following databases:

- PHARMO Database Network
- National Registers in Denmark
- National Registers in Sweden

A description of each database is provided in the following sections; further details are provided from the feasibility report, dated 1 November 2013, and in [ANNEX 5](#). The study will be conducted by using data on drug dispensings and disease occurrence routinely collected on an ongoing basis for large population-based automated health care databases in the Netherlands, Denmark, and Sweden (see [Table 1](#) and [Table 2](#) for characteristics of these databases). New users will be characterised in terms of past medical history and use of medications. Off-label prescribing will be evaluated for those new users for whom general practitioner diagnoses are available. An overview of the information on diagnoses and procedures by data source is shown in the table below ([Table 8](#)).

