#### 9.4.1.1 Database characteristics

The PHARMO Database Network consists of multiple databases containing data files on approximately 3.2 million community-dwelling inhabitants in geographically defined areas covering approximately 20% of the Netherlands. Data sources include information from general practitioners (GPs), community pharmacies, hospitals, and laboratory sources.

The patients covered in each database are not necessarily included in all of the databases, as some of the geographical areas overlap partially, but if they are in more than one database, they can be linked to construct the medical history as shown in [Figure 3](#). Thus, high-quality research can be conducted with ascertainment of patient demographics, drug dispensings, hospital morbidity, clinical laboratory results, and date of death.

The dispensing (outpatient pharmacy) database covering 3.2 million individuals can use a validated algorithm to identify patients with COPD, asthma, or other respiratory conditions. All patients are linked with the hospitalisation database (100% overlap between outpatient

and hospitalisation database). Approximately 440,000 patients can be linked to GP data for severity indicators as recorded by the GP.

GP = general practitioner.

Figure 3 Schematic overview of overlap example among databases included in the PHARMO Database Network

The GP database covering 1.4 million individuals has information as recorded by the GP, including forced expiratory volume in 1 second (FEV1) and spirometry data. Approximately half of the population (440,000) in the GP database can be linked to both dispensing (outpatient pharmacy) and hospitalisation data.

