| Clinical indication                              | For approximately 440,000 PHARMO subjects (included in outpatient database), via linkage to GP files and proximity of clinical diagnoses; for all subjects in GP database | Not recorded but may be surmised based on GP diagnoses for GP-linked practices and proxies (i.e., prescribed medication and hospital discharge diagnosis history) for not-linked practices | Not recorded but may be surmised based on GP diagnoses for GP-linked practices and proxies (i.e., prescribed medication and hospital discharge diagnosis history) for not-linked practices |
| Prescriber characteristics                       | GP vs. specialist   | GP vs. specialist  | Profession
Level of education
Speciality   |

Table 8 (con't) Overview of the study databases

| Data Element        | PHARMO (Netherlands)  | National Registers, Denmark  | National Registers, Sweden  |
|----------------------------|--|---|--|
| Outpatient diagnosis       | For all PHARMO subjects (included in outpatient databases): main diagnoses in ICD-9-CM for all admissions for > 24 hours and admissions for < 24 hours for which a bed is required; for subcohort of GP database patients with linkage to outpatient pharmacy database | Hospital outpatient diagnoses
General practitioner diagnoses for about 1 million population recorded via ICPC coding | Hospital diagnoses.
General practitioner diagnoses for the counties for Stockholm and Göteborg recorded via ICPC coding |
| Hospital diagnosis         | Main hospital diagnostic/surgical procedures   | Yes   | Yes  |
| Procedure codes            | Available for approximately 1 million of pharmacy file patients; GP laboratory tests for all patients in GP database   | Yes, ICD-10   | Yes, NCSP version 1.16:2012  |
| Pulmonary function testing | With difficulty  | From hospital clinics and also from primary care when recorded  | From hospital clinics and also from primary care when recorded   |
| Information on death       | Fact and date of death, Mortality Register   | Fact, date, and underlying cause of death available in National Death Register  | Fact, date, and underlying cause of death available in National Death Register   |
| Access to medical records  | Variable   | No  | No   |

Table 8 (con't) Overview of the study databases

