### 9.7.1 Main analysis

### 9.7.2 Indication and potential off-label prescribing

Number and proportion of new users for each indication (COPD only, COPD and asthma, asthma only, and no COPD or asthma) associated with the initiation of treatment.

This analysis will be conducted using data linked to diagnoses recorded by general practitioners (primary care information):

- PHARMO-GP, covering about 440,000 population
- Danish General Practice Database, covering about 1 million population
- Swedish General Practice Database for the counties of Stockholm and Göteborg

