## **9.10 OTHER ASPECTS**

### **9.10.1 Bias**

The use of hospital outpatient and/or inpatient discharge diagnoses can overestimate potential off-label prescribing. For this reason, and because use of hospital discharge diagnoses does not ascertain patients diagnosed with COPD who are not hospitalised, off-label use will be assessed in the subset of new users linked to the general practice (primary care) registers. In the three countries primary care data are only available for a subset of the population.

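### The SAP's main off-label analysis sets no GP-linkage condition, so on-label use is likely understated and potential off-label use likely overstated in Denmark and in non-GP PHARMO; report by type of diagnosis capture

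*SAP*

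**What the plan says.** **Protocol v2.0.** Section 9.4 states: "Off-label prescribing will be evaluated for those new users for whom general practitioner diagnoses are available". Sections 9.2, 9.3.2 and 9.7.2 set the same limit. Section 9.10.1 gives the reason. Hospital diagnoses can overestimate off-label prescribing and miss COPD patients who are never admitted, so "off-label use will be assessed in the subset of new users linked to the general practice (primary care) registers".

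**SAP.** Section 6.3 admits any new user with a first dispensing, one year of enrolment and valid age and sex. Section 7.5.1 then classifies by age and recorded diagnosis: children are off-label, adults with COPD on-label, adults with asthma but no COPD off-label, and for the remainder, "All adults with no COPD and no asthma diagnosis will be classified as potential off-label". Neither section mentions GP linkage. Results are planned overall and by age group, with a Clopper-Pearson 95% interval for on-label and off-label prevalence.

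**Diagnosis capture (SAP Section 3 and Table 2).** Denmark has hospital inpatient and hospital outpatient-clinic diagnoses and no GP diagnoses. PHARMO covers about 4 million patients, of whom about 1 million have GP data. It has no hospital outpatient diagnoses, so its non-GP patients have inpatient codes only.

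**SAP 7.3** repeats the overestimation warning and answers it with algorithms adapted to each source and a description of other respiratory conditions and potential COPD.

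**The concern.** This is the main outcome. SAP 5.1 defines COPD and asthma by recorded codes, and SAP 5.3 and 6.5 treat the absence of a code as absence of the condition. A COPD patient managed only in general practice therefore leaves the on-label count in Denmark and in non-GP PHARMO. Without an asthma code that patient becomes potential off-label; with one, off-label.

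The interval describes sampling error only. A narrow interval around a prevalence shifted by missing diagnoses would look more secure than it is. In PHARMO, an unsplit figure would mix two levels of capture.

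**Working it through.** **1. What the safeguards can do.**
- Source-adapted algorithms (SAP 7.3) cannot recover GP diagnoses that a source does not hold.
- Profile review (SAP 5.1) lists GP diagnoses only where the source has them. In Denmark it sees the same hospital codes plus dispensings. It may lead to a changed algorithm, but no rule for reclassification is given.
- *Probable COPD* is described within the potential off-label class. SAP 7.5.1 moves nobody from there to on-label.
- Protocol 9.4.1.1 says the PHARMO dispensing database "can use a validated algorithm to identify patients with COPD, asthma, or other respiratory conditions", and Protocol Table 8 mentions "proxies (i.e., prescribed medication and hospital discharge diagnosis history) for not-linked practices" for Denmark. The available SAP text adopts neither for classification.

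**2. Direction for on-label use.** Let Se be the share of COPD users with a qualifying COPD code and PPV the share of coded users who have COPD. True positives counted both ways give

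observed on-label = true on-label × Se / PPV.

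On-label use is understated whenever Se < PPV. Protocol 9.3.2.1 reports for Denmark that "the PPV for the hospital discharge diagnosis of COPD (ICD-10 code J44) was 92"%. If that held in new users and for the wider SAP code list (an assumption), understatement needs only Se < 0.92. The documents give no Se. SAP 7.3 says that COPD is managed mainly in primary care and that many patients may never have been hospitalised, which makes a lower Se likely but does not measure it.

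**3. Direction for asthma-only off-label.** This class gains COPD-plus-asthma patients whose COPD is not coded and loses asthma patients whose asthma is not coded. With asthma sensitivity a, COPD sensitivity s and independent recording,

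observed asthma-only = a × [share with both × (1 − s) + share with asthma only].

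Take assumed true shares of 20% with both and 10% with asthma only. The observed value exceeds 10% only if a > 0.10 / (0.30 − 0.20s), that is a > 0.42 at s = 0.3 and a > 0.83 at s = 0.9. Over an assumed grid of s from 0.3 to 0.9 and a from 0.1 to 0.5, that region is (0.1 − 0.5 × ln 1.2) / (0.6 × 0.4) = 0.037, about 4%. Under these assumptions the class is mostly understated. None of these inputs is in the documents, so the direction stays uncertain.

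**4. Precision cost of a GP-linked main result in PHARMO.** Exact Clopper-Pearson limits reproduce all 20 cells of Protocol Table 9 (for example 30/300 gives 6.8 to 14.0 and 500/5,000 gives 9.2 to 10.9), so the same method is used here.

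Inputs: 1,200 indacaterol users in PHARMO (Protocol Table 8; there are no olodaterol counts) and an assumed 80% on-label. The GP-linked share is 1/4 million = 25% from the SAP. Protocol 9.4.1.1 gives "440,000 patients can be linked to GP data" out of 3.2 million, or 13.75%.

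| Set | x/n | 95% interval, % | Width, points | Ratio |
|---|---|---|---|---|
| All PHARMO | 960/1,200 | 77.62 to 82.23 | 4.61 | 1 |
| GP-linked 25% | 240/300 | 75.02 to 84.38 | 9.36 | 2.03 |
| GP-linked 13.75% | 132/165 | 73.08 to 85.81 | 12.74 | 2.77 |

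Widths and ratios use unrounded limits. The 1,200 are users, not new users, and the 25% and the 1,200 come from different states of the database. The ratio is driven mainly by the linked share.

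**The case against.** **The restriction may have been lifted openly.** The SAP uses France instead of Sweden, omits the Danish GP database, gives different PHARMO coverage and refers to a core final study protocol. Section 4 lists none of these differences, which suggests it was written against a version later than v2.0. A reader might infer an undisclosed change; the documents do not support that. The request reduces to citing the protocol version that made it.

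**A PHARMO split may already exist.** In the sentence on evaluating off-label use, SAP Section 5 gives separate look-back dates for the total PHARMO set and the GP subset. It refers to Section 9.2 for database-specific detail. Section 9.2 and the table shells are not in the available text, so the absence of a split cannot be established. This stands, and the fix allows for it.

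**Denmark is partly handled.** Analyses run by data source, so *overall* in 7.5.1 most naturally means all ages, not pooled countries. SAP 7.3 states the bias and its direction. Patients with neither diagnosis are called potential off-label and kept apart from off-label, *probable COPD* is described among them, and SAP 7.5.2 plans to report algorithm against profile review. All of this stands. It leaves the on-label estimate low and the bias unmeasured.

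**The size is not known.** A reader might put a range of sensitivities through the formula and quote the result as the likely bias. Such ranges only restate the assumed inputs and are not offered as evidence here.

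**Conclusion.** The point holds in limited form. In the available text, the SAP classifies all new users with no GP-linkage condition. Both documents say that hospital diagnoses can overestimate off-label use, and the listed safeguards neither recover missing GP diagnoses nor move anyone to on-label. On-label use is therefore likely understated, and potential off-label use likely overstated, in Denmark and in non-GP PHARMO. The effect on asthma-only off-label is uncertain. The Clopper-Pearson interval does not cover the error.

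No size can be stated, because the documents give no sensitivity of COPD recording for any source. A reader might also conclude that the Danish results should be dropped. That does not follow: they are analysed separately and remain informative if labelled correctly. This should be fixed, with medium confidence, because Section 9.2 and any later protocol could change the PHARMO part.

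**What to change.** 1. **PHARMO.** In 7.5.1, report GP-linked and non-GP new users separately, with GP-linked as the main PHARMO result; if Section 9.2 already does this, cite it. The main interval becomes about 2.0 to 2.8 times as wide as in the full sample, under the illustrative counts above. The non-GP estimate stays beside it. The split also thins the naïve/switcher and age-group cells for both drugs.
2. **Same-patient comparison.** In PHARMO-GP, run the inpatient-only algorithm and the GP-plus-hospital algorithm on the same patients and report the 3 × 3 cross-classification (COPD, asthma only, neither). This indicates the bias in non-GP PHARMO. For Denmark, which also has outpatient-clinic codes, use it qualitatively only. The cost is one extra run in data already held.
3. **Denmark.** Keep it. Label it hospital-diagnosis-only with potential off-label likely overestimated, and add a sensitivity row showing potential off-label with and without *probable COPD*. The row is a subtraction from output already planned.
4. **Provenance.** Cite the protocol version that lifted the GP-linkage restriction, if one did.

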7.5.2 Patient profile review to evaluate COPD and asthma algorithms

A description of the patient profile review process is presented in Section [5.1](#). Patient profiles will be created on a random sample, stratified by age (18-39 years, ≥ 40 years) and sex, of 100 new users of each study drug olodaterol and indacaterol. Results of the manual review of the patient profiles will be described and compared with the treatment indications identified through the electronic algorithms based on medical codes. These results will be described in the study report. Results reporting COPD, asthma, and “no COPD no asthma” as identified by the electronic algorithm and after patient profile review will be presented (Shell Table 11).

Proprietary confidential information © 2017 Boehringer Ingelheim International GmbH or one or more of its affiliated companies

